5.1.12 Urine studies

Urine dipstick; if ++ or higher, random urine protein and creatinine, urine protein to creatinine ratio

5.1.13 12-lead ECG

5.1.14 Pregnancy test (for females of child bearing potential)

See section 3.1.8.1 for definition.

5.1.15 Tumor assessment

To be performed with computed tomography of the chest with contrast only (if contrast allergy, CT chest may be done without contrast), and abdomen/pelvis with contrast per physician discretion. CT abdomen/pelvis may be replaced with MRI Abdomen/pelvis per clinical judgement of the treating physician. Additional imaging is indicated at baseline if there is clinical suspicion for other organ involvement (e.g., MRI or CT brain and bone scan).

Imaging is to be performed at baseline within 28 days of starting treatment

5.1.16 Serious Adverse Events Assessment

5.2 Registration Procedures for participating sites only

Prior to confirmation of registration the below items must be emailed via secure email to the initiating site for review and approval.

- 1. Redacted source documentation required to confirm eligibility (including but not limited to):
 - a. Pathology report
 - b. Physical exam including ECOG, medical and oncology history
 - c. All screening labs
- 2. Signed eligibility criteria

All items must be emailed via secure email to ([contact] and [contact]) UCI CFCCC at least 3 business days before planned treatment start date.

Upon receipt of all required documents, UCI CFCCC will provide confirmation of registration. Subjects may not begin study treatment without confirmation of registration.

5.3 Procedures During Treatment

5.3.1 Prior to Each Treatment Cycle

- · Physical exam, vital signs
- Hematology
- Serum chemistries
- · Adverse events
- · Study drug accountability
- · Review previous and concomitant medications
- Pregnancy Test (if applicable)

Site must maintain an accurate and timely record of dispensing of study drug to subject, and receipt of all study drug and pill diaries.

5.3.2 Within 30 days after treatment termination

- · Physical exam, vital signs
- Hematology
- Serum chemistries
- Adverse events
- · Review previous and concomitant medications
- Pregnancy Test (if applicable)

5.3.3 Tumor Assessments

 To be completed every 8 weeks (+/- one week) during first year of treatment and every 3 months (+/- one week) after the first year until patient comes off study

5.4 Follow-up Procedures

Patients will be followed every three months after completion of (or early withdrawal from) study treatment until death or up to 18 months after the last patient is enrolled, whichever comes first.

• Review of systems and determination of live status (either in clinic during standard visit or by phone)

5.5 Time and Events Table

Baseline evaluations are to be conducted within 1 week prior to administration of protocol therapy. Scans and x-rays must be done ≤4 weeks prior to the start of therapy. In the event that the patient's condition is deteriorating, laboratory evaluations should be repeated within 48 hours prior to initiation of the next cycle of therapy.

	Baseline -28 to -1 days	C1D1 +/- 3 days	At every cycle (21 days) +/- 3 days	q 8 Weeks for first year, q 3 months after the first year +/- 1 week	Off Treatment	Follow- up (q 3 months until death or up to 18 months after last patient is enrolled, whicheve r occurs first) +/- 14 days
Assessment						
Informed Consent	Χ					
History and PE	Χ	Х	X		X	
Concomitant Medications	Х	Х	Х		X	
Performance Status	Х	Х	Х		Х	
Adverse Events	X**	Х	Х		Х	
Tumor Measurements	Х			Х		
CT CAP or CT chest/MRI Abd/Pelvis	Х			Х		
CBC / CMP / UA / UPCR	Х	X	Х		Х	
PT/INR, PTT	Х	Х	X***			
TFTs (TSH, free T3, free T4)	Х	Х	X***			
CEA and CA 19-9 (optional)****			Х			
12-lead ECG	Х	Χ	X***		Х	
Pregnancy Test*	Х	Х	X***		Х	
Review of systems						Х
Study Drug Accountability			Х		Х	

^{*}Urine or serum pregnancy test is done according to local institutional standard and should be obtained ONLY in women of child-bearing potential.

^{**} Only Serious Adverse Events will be assessed and reported during baseline

^{***} To be done Day 1 of Weeks 3, 6, 9 and then every 4-6 weeks

^{****} This is an optional component and should only be collected if done according to local

institutional standards.

5.6 Removal of Subjects from Study

Patients can be taken off the study treatment and/or study at any time at their own request, or they may be withdrawn at the discretion of the investigator for safety, behavioral or administrative reasons. The reason(s) for discontinuation will be documented and may include:

- 5.5.1 Patient voluntarily withdraws from treatment (follow-up permitted):
- 5.5.2 Patient withdraws consent (termination of treatment and follow-up);
- 5.5.3 Patient is unable to comply with protocol requirements;
- 5.5.4 Subjects who cannot tolerate the minimum protocol-specified dose of study treatment will have study treatment discontinued;
- 5.5.5 Patient demonstrates disease progression or subject no longer experiences clinical benefit as determined by the investigator (unless continued treatment with study drug is deemed appropriate at the discretion of the investigator);
- 5.5.6 Patient experiences toxicity, intercurrent illness, or specific conditions in section 4.2 that makes continuation in the protocol unsafe;
- 5.5.7 Treating physician judges continuation on the study would not be in the patient's best interest;
- 5.5.8 Patient becomes pregnant or patient is breastfeeding (pregnancy to be reported along same timelines as a serious adverse event);
- 5.5.9 Development of second malignancy (except for basal cell carcinoma or squamous cell carcinoma of the skin) that requires treatment, which would interfere with this study;
- 5.5.10 Sexually active subjects who refuse to use medically accepted barrier methods of contraception during the course of the study and for 4 months after discontinuation of study treatment
- 5.5.11 Subjects who cannot tolerate the minimum protocol-specified dose of study treatment will have study treatment discontinued
- 5.5.12 If a subject does not recover from his or her toxicities to tolerable Grade ≤ 2 within 6 weeks, the subject will have study treatment discontinued unless there is unequivocal evidence that the subject is benefitting. In this situation, a subject may be able to restart therapy with a dose reduction of the toxicity and with agreemtn of the investigator
- 5.5.13 Request by regulatory agencies for termination of treatment of an individual subject or all subjects under the protocol
- 5.5.14 Lost to follow-up. If a research subject cannot be located to document survival after 3 attempts including 1 mailed certified letter, the subject may be considered "lost to follow-up." All attempts to contact the subject during the two years must be documented and approved by the Data Monitoring Committee.

6.0 Measurement of Effect

6.1 Antitumor Effect- Solid Tumors

Response and progression will be evaluated in this study using the new international criteria proposed by the Response Evaluation Criteria in Solid Tumors (RECIST) Committee [JNCI 92(3):205-216, 2000]. Changes in only the largest diameter (unidimensional measurement) of the tumor lesions are used in the RECIST v1.1 criteria.

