2.3 Endpoints

The primary endpoint is 6 months progression-free survival (PFS-6). The secondary endpoints are rates of drug-related grade 3-5 adverse events experienced during and up to four weeks after completion of study treatment. These will be assessed via NCI's CTCAE v5.0 toxicity criteria. Other secondary endpoints are best objective response rate by RECIST v1.1 in patients with measurable disease and overall survival.

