4.6 Duration of Therapy

In the absence of treatment delays due to adverse events, treatment may continue until:

- Disease progression as defined radiographic progression by RECIST v1.1 criteria OR death OR symptomatic progression as clinically determined by the treating physician
- Inter-current illness that prevents further administration of treatment
- Unacceptable adverse event(s)
- Treatment held for more than 28 days
- Patient decides to withdraw from the study, OR
- General or specific changes in the patient's condition render the patient unacceptable for further treatment in the judgment of the investigator.

4.7 **Duration of Follow Up**

Patients will be followed every 3 months until death or 18 months after the last patient is enrolled, whichever occurs first. Patients removed from treatment for unacceptable adverse events will be followed until resolution or stabilization of the adverse event. Follow-up after removal from treatment is every 3 months (either clinic visit or phone call).

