6.1.2 Disease Parameters

Measurable disease. Measurable lesions are defined as those that can be accurately measured in at least one dimension (longest diameter to be recorded) as \geq 20 mm with conventional techniques (CT, MRI, x-ray) or as \geq 10 mm with spiral CT scan. All tumor measurements must be recorded in millimeters (or decimal fractions of centimeters).

Note: Previously irradiated lesions are non-measurable except in cases of documented progression of the lesion since the completion of radiation therapy.

Non-measurable disease. All other lesions (or sites of disease), including small lesions (longest diameter <20 mm with conventional techniques or <10 mm using spiral CT scan), are considered non-measurable disease. Bone lesions, leptomeningeal disease, ascites, pleural/pericardial effusions, lymphangitis cutis/pulmonis, inflammatory breast disease, abdominal masses (not followed by CT or MRI), and cystic lesions are all non-measurable.

Note: Cystic lesions that meet the criteria for radiographically defined simple cysts should not be considered as malignant lesions (neither measurable nor non-measurable) since they are, by definition, simple cysts.

'Cystic lesions' thought to represent cystic metastases can be considered as measurable lesions, if they meet the definition of measurability described above. However, if non-cystic lesions are present in the same patient, these are preferred for selection as target lesions

Target lesions. All measurable lesions up to a maximum of 3 lesions per organ and 6 lesions in total, representative of all involved organs, should be identified as **target lesions** and recorded and measured at baseline. Target lesions should be selected on the basis of their size (lesions with the longest diameter) and their suitability for accurate repeated measurements (either by imaging techniques or clinically). A sum of the longest diameter (LD) for all target lesions will be calculated and reported as the baseline sum LD. The baseline sum LD will be used as reference by which to characterize the objective tumor response.

Non-target lesions. All other lesions (or sites of disease) including any measurable lesions over and above the 6 target lesions should be identified as **non-target lesions** and should also be recorded at baseline. Measurements of these lesions are not required, but the presence or absence of each should be noted throughout follow-up.

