6.1.3 Methods for Evaluation of Measurable Disease

All measurements should be taken and recorded in metric notation using a ruler or calipers. All baseline evaluations should be performed as closely as possible to the beginning of treatment and never more than 28 days before the beginning of the treatment.

The same method of assessment and the same technique should be used to characterize each identified and reported lesion at baseline and during follow-up. Imaging-based evaluation is preferred to evaluation by clinical examination when both methods have been used to assess the antitumor effect of a treatment.

Conventional CT and MRI. These techniques should be performed with cuts of 10 mm or less in slice thickness contiguously. Spiral CT should be performed using a 5 mm contiguous reconstruction algorithm. This applies to tumors of the chest, abdomen, and pelvis. MRI is also acceptable in certain situations (e.g. for body scans). Scans will be done within 28 days prior to cycle 1 and after that every 8 weeks (+/- 7 days) until end of treatment.

Cytology, Histology. These techniques can be used to differentiate between partial responses (PR) and complete responses (CR) in rare cases (e.g., residual lesions in tumor types, such as germ cell tumors, where known residual benign tumors can remain).

The cytological confirmation of the neoplastic origin of any effusion that appears or worsens during treatment when the measurable tumor has met criteria for response or stable disease is mandatory to differentiate between response or stable disease (an effusion may be a side effect of the treatment) and progressive disease.

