6.1.4 Response Criteria

6.1.4.1 Evaluation of Target Lesions

Complete Response (CR): Disappearance of all target lesions, determined by two separate observations conducted not less than 4 weeks apart. There can be no appearance of new lesions.

Partial Response (PR): At least a 30% decrease in the sum of the longest diameter (LD) of target lesions, taking as reference the baseline sum LD. There can be no appearance of new lesions.

Progressive Disease (PD): At least a 20% increase in the sum of the LD of target lesions, taking as reference the smallest sum LD recorded since the treatment started, or the appearance of one or more new lesions.

Stable Disease (SD): Neither sufficient shrinkage to qualify for PR nor sufficient increase to qualify for PD, taking as reference the smallest sum LD since the treatment started.

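### Section 6.1 cites a 2000 publication but calls its rules RECIST v1.1, and its progression rule for PFS-6 has no minimum absolute increase, so a 10 mm tumour sum progresses at +2 mm

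*Combined protocol and SAP*

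**What the plan says.** **Which criteria.** Section 6.1 says response and progression follow the criteria of the "Response Evaluation Criteria in Solid Tumors (RECIST) Committee [JNCI 92(3):205-216, 2000". Its next sentence says that only changes in the largest diameter of the "tumor lesions are used in the RECIST v1.1 criteria". Elsewhere v1.1 is named for objective response, in 2.2.2 and in 2.3 ("best objective response rate by RECIST v1.1 in patients with measurable disease"), and in 4.6, where treatment may continue until, among other events, "radiographic progression by RECIST v1.1 criteria".

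**The written-out rules.** Section 6.1.2 accepts a lesion of 10 mm on spiral CT (20 mm by conventional technique) as measurable. It takes as targets "All measurable lesions up to a maximum of 3 lesions per organ and 6 lesions in total", with no minimum number above one. Section 6.1.4.1 defines progressive disease as "At least a 20% increase in the sum of the LD of target lesions", relative to the smallest sum since treatment started, or as a new lesion. No section states a minimum increase in millimetres.

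**The route to the primary endpoint.** Section 6.1.6 defines progression for PFS as death, radiographic progression according to 6.1.4.3, or clinical deterioration that the investigator attributes to the disease. The table in 6.1.4.3 uses the target-lesion categories of 6.1.4.1. Section 9.1 makes PFS-6 the primary efficacy endpoint and refers back to the PFS section for progression.

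**The concern.** One set of rules is given two sources, a publication dated 2000 and the label v1.1, and the protocol does not say which governs if they differ. A site reader who consults an outside text rather than Section 6.1 cannot tell which text to use.

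Separately, the rule as printed is purely relative. When the smallest sum is small, 20% of it is one or two millimetres, and a change of that size is enough to end PFS. Small sums arise most easily in patients whose tumours have shrunk, who are also the likeliest PFS-6 successes. The trial is decided by very small counts (at least 2 of 19, then at least 4 of 27), so one success lost to a marginal measurement can matter.

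**Working it through.** **1. The plan's own figures.** Inputs from 9.2: p0 = 0.05, p1 = 0.20, continue if at least 2 of 19, reject the null if at least 4 of 27.

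- P(X ≤ 1 | 19, 0.05) = 0.95^19 + 19 × 0.05 × 0.95^18 = 0.377 + 0.377 = 0.755. The plan states 0.75.
- Exact two-stage type I error is 0.0414 and power is 0.803. The plan states 5% and 80%.

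The design reproduces and is not in dispute.

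**2. Smallest increase that counts as progression.** From 6.1.4.1, the increase is 0.20 × smallest sum. The second column applies the printed rule. The last two use max(0.20 × sum, m) with an assumed floor m, because the documents give none.

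| Smallest sum | As written | m = 3 mm | m = 5 mm |
|---|---|---|---|
| 7 mm (10 mm after a 30% decrease) | 1.4 mm | 3 mm | 5 mm |
| 10 mm (one lesion, spiral CT minimum) | 2.0 mm | 3 mm | 5 mm |
| 20 mm (one lesion, conventional minimum) | 4.0 mm | 4 mm | 5 mm |
| 25 mm | 5.0 mm | 5 mm | 5 mm |
| 50 mm | 10.0 mm | 10 mm | 10 mm |

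A floor changes the rule only when the smallest sum is below m / 0.20. That is 3 / 0.20 = 15 mm for a 3 mm floor and 5 / 0.20 = 25 mm for a 5 mm floor.

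**3. Weight of one patient.** 1/19 = 5.3 percentage points at stage 1, and 1/27 = 3.7 points at the end. At a true PFS-6 of 20%, the chance of exactly 2 successes in 19 is 171 × 0.04 × 0.8^17 = 0.154. In that case one success wrongly called progression fails the stage 1 rule.

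**4. Direction and possible size.** Calling progression too readily turns successes into failures and never the reverse. If a fraction f of true successes is lost, the observed rate is p × (1 − f). The documents give no value for f, so these are illustrations only, under the 19/27 rule:

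| f | Observed rate when the true rate is 20% | Power | Type I error (true rate 5%) |
|---|---|---|---|
| 0 | 20% | 80.3% | 4.1% |
| 5% | 19% | 76.7% | 3.5% |
| 10% | 18% | 72.6% | 3.0% |
| 20% | 16% | 63.0% | 2.0% |

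**5. The text of Section 6.1 itself.** Two places suggest that its rules were not drawn cleanly from one source. Section 6.1.2 lists cystic lesions as non-measurable and then allows presumed cystic metastases to be measurable. Section 6.1.4.2 uses stable disease for persisting non-target lesions, while 6.1.4.3 advises against that label when no lesion can be measured.

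**The case against.** The best defence is that Section 6.1 is the only operational rule set in the document and carries the v1.1 label itself, so the dated citation is a reference slip. PFS-6 then has one defined radiographic route, from 6.1.6 to 6.1.4.3. Much of this stands. Four stronger readings are tempting, and the documents do not support them:

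- **The primary endpoint is itself defined by v1.1.** It is not. Section 2.3 names v1.1 only for objective response, and 6.1.6 points to 6.1.4.3. The label reaches progression only through 6.1, 4.6 and the local-treatment restriction in 4.1.2.2.
- **Two rule sets give two progression dates for one patient.** This cannot be shown. The v1.1 rules are not reproduced, so neither a difference from 6.1 nor the size of any absolute minimum can be read from the documents.
- **Such growth is below scan resolution.** Section 6.1.3 says "Spiral CT should be performed using a 5 mm contiguous reconstruction algorithm". That is a reconstruction setting, and the document does not state it to be the measurement error of a longest diameter.
- **Every patient with a nadir sum under 25 mm is affected.** The cutoff depends on an assumed 5 mm floor. A PFS-6 result changes only if three things hold: the rise is at least 20% but under the floor; there is no new lesion, non-target progression, clinical deterioration or death; and removing the call carries the patient past six months.

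It is also fair to say that a single 10 mm target is the minimum case. Section 6.1.2 takes all measurable lesions up to six, so many sums will be larger. The value of one patient in percentage points holds for any misclassification and says nothing about how often this one occurs.

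The objection leaves two facts untouched: the citation and the label disagree, and the printed progression rule behind the primary endpoint has no absolute minimum.

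**Conclusion.** The point holds in a limited form. Section 6.1 gives its rules two sources, and the progression rule that feeds PFS-6 allows a call at +2 mm for a 10 mm sum or +1.4 mm from a 7 mm nadir. The arithmetic needs only the 20% rule and the 10 mm measurability limit, both printed.

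How many patients this affects is unknown, because the documents give neither a distribution of tumour sums nor a measurement error. The effect runs one way: it can lower observed PFS-6 and power, and it cannot create a false positive against the 5% null. The power losses above are illustrations, and the 3 mm and 5 mm floors are assumptions. A reader should not conclude that PFS-6 has been shown to be materially biased. The case for acting is that the rule is stated, sits behind the primary endpoint and is cheap to put right before counts as small as 2 of 19 and 4 of 27 are read.

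**What to change.** 1. Name one RECIST version throughout, correct the citation in 6.1, and make the measurability, target-lesion and progression text in 6.1.2 to 6.1.4 match that version.
2. For the PFS-6 endpoint, require a minimum absolute increase in the sum as well as the 20%. Take its size from the named version. For scale, a 3 mm floor would affect only sums below 15 mm and a 5 mm floor only sums below 25 mm.
3. State in 6.1.6 that PFS uses this definition.
4. Reconcile 4.6 with it. Which rule should govern stopping treatment is for the sponsor and investigators, and this review does not choose one.

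**Cost.** Text edits, plus re-tabulation of diameters that 6.1.2 already requires in millimetres. If the chosen version changes which lesions are targets, some existing scans may have to be re-read, because 6.1.2 does not require measurements of non-target lesions. No new imaging is needed.

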6.1.1 Definitions

Evaluable: All patients receiving cycle 1, day 1 of the protocol treatment.

Evaluable for toxicity. All patients will be evaluable for toxicity from the time of their first treatment with study drug.

Evaluable for objective response. Only those patients who have measurable disease present at baseline, have received at least one cycle of therapy, and have had their disease re-evaluated will be considered evaluable for response. These patients will have their response classified according to the definitions stated below. (Note: Patients who exhibit objective disease progression prior to the end of cycle 1 will also be considered evaluable.)

Evaluable Non-Target Disease Response. Patients who have lesions present at baseline that are evaluable but do not meet the definitions of measurable disease, have received at least one cycle of therapy, and have had their disease re-evaluated will be considered evaluable for non-target disease. The response assessment is based on the presence, absence, or unequivocal progression of the lesions.

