9.0 STATISTICAL CONSIDERATIONS

9.1 Study Design/Study Endpoints

This is a single-arm, open label, phase-II trial designed as a pilot to see if the treatment regimen is worthy of further study. Specifically, the trial is designed as the first stage of a Simon two-stage, minimax design[39]. The goal is to gather evidence on efficacy or futility of the study treatment in this study population, while monitoring toxicity. The two-stage approach offers economy and exposes the fewest possible participants to potential harm without substantial benefit, with control of the probability of errors in decisions.

Primary Endpoint: For efficacy the primary endpoint is progression-free survival at six months (PFS-6), dating from the first dose of study treatment. Progression is defined and determined as given in Section 61.6. For toxicity, the primary endpoint is the number of participants showing serious toxicity during their participation in the trial. Serious toxicities are given in Section 7.0.

Efficacy Null Hypothesis: Based on current outcomes for this study population[25][26], the null hypothesis is that 5% of evaluable patients will be progression-free at six months.

Efficacy Alternative Hypothesis: Based on our clinical judgment and aspirations, we anticipate that 20% (or more) of evaluable participants will be progression-free at six months. In our view, 20% progression-free at six months is the smallest advance that would be judged clinically worthwhile.

Secondary endpoints:

- Overall survival, defined as time from starting treatment to death from any cause.
- Objective response rate in patients with measurable disease as defined in section 6.0
- Safety as described in the adverse events in section 7.0

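### The response-evaluable rule in section 6.1.1 removes treated patients with no post-baseline re-evaluation from the ORR denominator, which biases ORR upward

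*Combined protocol and SAP*

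**What the plan says.** The endpoint is described in three places, and they do not give the same denominator.

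- Section 2.3 lists "best objective response rate by RECIST v1.1 in patients with measurable disease". It does not mention re-evaluation.
- Section 9.1 lists "Objective response rate in patients with measurable disease as defined in section 6.0", and so sends the reader to section 6.0.
- Section 6.1.1 restricts response evaluability to patients with measurable disease who "have received at least one cycle of therapy, and have had their disease re-evaluated will be considered evaluable for response". A note adds: "Patients who exhibit objective disease progression prior to the end of cycle 1 will also be considered evaluable".

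Section 6.1.1 also has a wider general set: "Evaluable: All patients receiving cycle 1, day 1 of the protocol treatment". The ORR text does not use it.

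The assessment schedule matters here. Section 5.3.3 sets tumor assessments as follows: "To be completed every 8 weeks (+/- one week) during first year of treatment". Neither section 5.3.2 nor the Off Treatment column of the section 5.5 table lists a tumor assessment. Section 4.6 allows treatment to end on "symptomatic progression as clinically determined by the treating physician", which needs no scan. Section 4.9 rules out replacing patients.

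**The concern.** Membership of the response set depends partly on outcome. A patient who does badly before the first scan is less likely to be re-evaluated, and without a re-evaluation is not counted. Such a patient can never add to the numerator, so each removal can only raise the reported rate or leave it at zero.

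The exception does not cure this. Showing objective progression already presupposes an assessment, so in practice the note waives the one-cycle condition and does not reach patients with no assessment. It also stops at the end of cycle 1 (day 21), about five weeks before the week 8 scan.

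The plan also treats the same event differently across endpoints. Section 6.1.6 counts death, and clinical deterioration attributed to disease, as PFS events. Section 6.1.4.3 records deterioration without objective evidence under a separate label, and its table for patients with target lesions has no category for an unassessed patient. One patient can therefore be a failure for PFS and absent from ORR.

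What is at stake is how the activity estimate reads. With at most 27 patients, a few removals visibly move the rate, and always in the regimen's favour.

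**Working it through.** **The plan's own figures.** The plan states no target, precision or sample size for ORR. Its only design figures concern PFS-6. For 19 patients and a true rate of 5%, the probability of at most one success is 0.95^19 + 19 × 0.05 × 0.95^18 = 0.377 + 0.377 = 0.755, which agrees with the stated 0.75. Power at 20% for the 19/27 rule is 0.803 (stated 80%), and exact type I error is 0.041 (stated ceiling 5%). None of these uses the response-evaluable set.

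**Direction.** Let N be treated patients with baseline measurable disease, k those with no re-evaluation, and r the responders.

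- All treated with measurable disease: r/N.
- Section 6.1.1 rule: r/(N − k).
- Ratio: N/(N − k), which exceeds 1 whenever k > 0. The reported rate rises whenever r > 0 as well.

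**Size, as illustration only.** The documents give neither k nor r, and eligibility does not require measurable disease. Assume all treated patients have it.

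| N | r | k = 0 | k = 2 | k = 5 |
|---|---|---|---|---|
| 27 | 3 | 3/27 = 11.1% | 3/25 = 12.0% | 3/22 = 13.6% |
| 27 | 4 | 4/27 = 14.8% | 4/25 = 16.0% | 4/22 = 18.2% |
| 19 | 3 | 3/19 = 15.8% | 3/17 = 17.6% | 3/14 = 21.4% |

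For N = 27 the ratio is 27/25 = 1.08 at k = 2 and 27/22 = 1.23 at k = 5. Exact 95% intervals for r = 3 are 2.4% to 29.2% (3/27), 2.5% to 31.2% (3/25) and 2.9% to 34.9% (3/22).

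**Is k of this order conceivable?** Assume exponential survival with two median survival times on active treatment quoted in section 1.1: 9.1 months (pembrolizumab, second line) and 5.7 months (trifluridine/tipiracil, third line or later). The share dead by 8 weeks (1.84 months) is 1 − 2^(−1.84/median):

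- 9.1 months: 13.1%, or 0.131 × 27 = 3.5 patients.
- 5.7 months: 20.1%, or 0.201 × 27 = 5.4 patients.

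This is not a bound in either direction. It ignores the required life expectancy above 3 months and any earlier re-evaluation, both of which lower k. It also leaves out patients who stop or withdraw alive and unassessed, who raise k.

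**How the protocol's quoted benchmarks are calculated.** In Table 8 (section 1.3) the non-colorectal rows sum to 59 only if the two patients marked NE are included, and the reported rate is 27/59 = 46%. Without them it would be 27/57 = 47.4%. The KEYNOTE-059 rate of 13.3% in the same section is 19/143, the whole stated subgroup. Both keep the full denominator.

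**The case against.** Several points on the other side have force.

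**The excluded group can be overstated.** A reader might infer that every patient who fails, stops or withdraws before week 8 is dropped. The documents do not support that. Section 6.1.4.3 asks that progression still be documented after treatment stops for deterioration. Section 5.3.3 continues assessments until the patient leaves the study, and section 5.6 separates stopping treatment from withdrawing consent. Section 6.1.3, however, ends scans with treatment, so the plan is unsettled here. Section 6.1.1 also speaks of receiving a cycle, not completing one, and of re-evaluation, not re-scanning. The point therefore covers only patients with no re-evaluation at all.

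**Section 9.1 can be read differently.** Its pointer to section 6.0 could attach to measurable disease alone, so that ORR already uses all such patients. Even then, section 6.1.1 says only re-evaluated patients have their response classified, and nothing says how the others count. The same sentence would be needed.

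**Non-response in an unassessed patient is a convention.** Someone who stopped for toxicity might have had shrinkage nobody saw. That is fair, but they are still not a documented responder, and the benchmarks above handle such patients in the same way.

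**Larger effects.** A reader might use the 3.6-month median survival also quoted in section 1.1, which gives about 30% dead by week 8 and a factor of 1.43. That median is from a placebo arm, and everyone here receives active treatment, so it is not a suitable basis.

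**Consequences.** A reader might infer that ORR will be tested against historical rates. No section says so. The historical comparison in section 9.1 concerns PFS-6, and section 9.3 rules out formal testing for secondary analyses. Sampling error also far exceeds the illustrated shifts.

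**Conclusion.** The point holds. Followed literally, section 6.1.1 gives an ORR biased upward by N/(N − k) whenever at least one patient responds and at least one treated patient with measurable disease is never re-evaluated. The direction is certain; the size cannot be computed from the documents. Two to five unassessed patients out of 27, with 3 responders, would add 0.9 to 2.5 percentage points, assuming all 27 have measurable disease. The bias is zero if nobody responds or everyone is re-evaluated.

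A reader might infer that the trial's go/no-go decision is compromised. It is not. PFS-6 counts death and disease-related clinical deterioration as failures, the general evaluable set is everyone given cycle 1 day 1, and the 19/27 rules do not use the response set. This is a correction that should be made to a descriptive secondary endpoint.

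**What to change.** In section 6.1.1, define the ORR denominator as all patients with measurable disease at baseline who received cycle 1 day 1. Count those without a post-baseline assessment as non-responders, and report their number and the reasons. Keep the response-evaluable subset as a labelled sensitivity analysis. Sections 2.3 and 9.1 can then refer to this one definition.

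The cost is a short text change. It needs no new data, visits or patients. The only downside is that the reported ORR may be slightly lower.
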